#### **All Subjects:**

**CTI ablation:** Ablation of the CTI may be performed in both Pulsed Field Subjects and Thermal Group Subjects using any approved catheter in subjects with a past history of cavo-tricuspid isthmus-mediated (typical) AFL, subjects who manifest typical AFL during a procedure or within the Blanking Period, or subjects who have inducible typical flutter. Bidirectional block should be demonstrated after the last CTI ablation.

The CTI ablation data will be documented in the CRF and does not constitute a Treatment Failure.

**Other Ablation:** Other ablation is not permitted under this protocol except when the Investigator determines that subject welfare requires ablation for an accessory pathway, AVNRT, treatment-emergent left AFL or incessant AT, using any approved ablation catheter. This decision and the associated ablation data will be documented in the CRF and does not constitute a Treatment Failure.

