### 3.4.12 Per Protocol Subjects

A Per Protocol (PP) Subject is a Safety or ITT Subject without major protocol deviations that would affect the completeness, accuracy and reliability of the study data. Major protocol deviations that exclude subjects from a PP Population are the following:

- Failure to meet any of the following study entry criteria:
  - Arrhythmia different than PAF (Inclusion Criterion 1)
  - Prior cardiovascular procedures, implants or conditions (Exclusion Criteria 3 and 4)
  - Medical conditions (Exclusion Criterion 11)
- Failure to receive the randomized ablation treatment for PVI as specified in this protocol (**Section 5.2 or Section 5.3**)
- Receipt of a prohibited study drug (amiodarone, except intra-procedurally to control an arrhythmia )
- In addition, the data of Severe COVID-19 Subjects will be censored beginning on the Onset Date of infection.

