#### 6.3.2 Acute Procedural Failure

The absence of Acute Procedural Success, including the use of any non-randomized energy modality for PVI.

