#### 7.4 Primary Effectiveness Endpoint

**Treatment Success:** The primary effectiveness endpoint is Treatment Success in MITT Subjects, defined as:

1. **Acute Procedural Success (Section 6.3.1) AND**
2. **Chronic Success**, defined as freedom from:
  - a. At the Index / Rescheduled Index Procedure: Use of a non-randomized treatment modality for PVI
  - b. After the Blanking Period:
    - i. Occurrence of any Detectable AF, AFL or AT (**Section 6.3.11**) (excluding CTI-dependent flutter confirmed by EP study)
    - ii. Any cardioversion for AF, AFL or AT (excluding for CTI-dependent flutter)
    - iii. Use of any Type I or Type III antiarrhythmic medication for the treatment of AF, AFL or AT
  - c. At any time:
    - i. Re-ablation for AF, AFL or AT (other than for CTI-dependent flutter)
    - ii. Use of amiodarone, except intra-procedurally to control an arrhythmia

Endpoint status will be assessed through the Month 12 Assessment (Day 360  $\pm$  30).

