16.3 Other Sensitivity Analyses

- A sensitivity analysis of the Primary Effectiveness Endpoint will also be conducted, in which subjects requiring ablation for an accessory pathway, AVNRT, treatment-emergent left AFL, or incessant AT are counted as treatment failures.
- As indicated in Section 9, the primary analysis for effectiveness will be conducted in the mITT population, but supportive analyses will also be conducted in the PP population. Similarly, as indicated in Section 10, the primary analysis for safety will be conducted in the Safety Population, supportive analyses will also be conducted in the PP population.
- For the primary effectiveness endpoint, Kaplan-Meier estimates of event rates will also be presented.

17 Heterogeneity/Poolability

Incidence of the primary safety and primary effectiveness endpoints will be evaluated for poolability across key subgroups. In particular, the primary endpoints will be examined for differences between sexes and sites. A specific categorization of sites is those that use RF as the control therapy and those that use cryoablation as the control therapy. Poolability of treatment effect over this factor (site uses RF, site uses cryo) will also be studied.

Poolability tests will be conducted with frequentist methods. For each factor of interest (sex, site), a logistic regression will be fit, with predictors Treatment Group, the factor, and their interaction. If the interaction p-value is significant at the level 0.15, further analyses will be conducted. At a minimum, any baseline variables found to differ between treatment groups and any baseline variables found to significantly predict a primary event (Treatment Response, or occurrence of CSE) in univariate analyses will be candidates for inclusion in logistic regression adjustment to see whether the apparent heterogeneity is explained by these factors. If so, analyses that adjust for these factors will be presented. If not, further analyses will be conducted, including presenting results separately by sex / site.

Sites with fewer than 8 subjects will be considered small sites. Poolability analyses will be summarized descriptively for all sites, but inferential tests of poolability across sites will exclude small sites. If there are many small sites, or many sites with 0 events, inferential tests of poolability across sites may not be conducted.

18 Other Planned Analyses

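### Index ablation that Protocol 5.2 prohibits is not a Treatment Failure under 7.4, and the SAP 16.3 check on extra ablation counts only the permitted exceptions

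*Protocol*

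**What the plan says.** **The prohibition.** Protocol 5.2 (All Subjects, Other Ablation) states: "Other ablation is not permitted under this protocol except when the Investigator determines that subject welfare requires ablation". The four exceptions are AVNRT, an accessory pathway, incessant AT and treatment-emergent left AFL. Of these exceptions it says: "This decision and the associated ablation data will be documented in the CRF and does not constitute a Treatment Failure". It gives no endpoint consequence for ablation outside them.

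**The primary endpoint.** The only index-procedure item under Chronic Success in Protocol 7.4 is "At the Index / Rescheduled Index Procedure: Use of a non-randomized treatment modality for PVI". Acute Procedural Failure (Protocol 6.3.2) is "The absence of Acute Procedural Success, including the use of any non-randomized energy modality for PVI". The ablation item that applies at any time covers re-ablation only.

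**The checks.**
- The nearest Per Protocol exclusion (Protocol 3.4.12) is "Failure to receive the randomized ablation treatment for PVI as specified in this protocol", followed by a reference to Section 5.2 or 5.3. SAP 4.1.12 is worded almost identically.
- SAP 16.3 adds a sensitivity analysis in which "subjects requiring ablation for an accessory pathway, AVNRT, treatment-emergent left AFL, or incessant AT are counted as treatment failures".
- Additional analysis 8 repeats Treatment Success without certain subjects. Protocol 7.6 removes those whose index procedure *required* atrial ablation other than PVI or CTI. SAP 9.3.8 removes those *receiving* extra ablation.

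**The concern.** A sensitivity analysis on extra ablation should capture the extra ablation most able to distort the comparison. As written, SAP 16.3 fails subjects whose operators followed the protocol, including those treated for AVNRT or an accessory pathway. It leaves as successes those who received lesions the protocol forbids.

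Operators know the assigned arm when they choose lesions (Protocol 5.7). If added lesions prevent recurrence, the primary test credits the benefit to the randomized system. More such lesions in the Pulsed Field arm would favour a false finding of non-inferiority; more in the Thermal arm would reduce power.

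The protocol closes this door elsewhere. Under 4.7.10, other sites may be ablated at a re-ablation because that subject already counts as a Treatment Failure. The index procedure has no matching rule.

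**Working it through.** **1. One subject traced through the rules.** Take a subject with all veins isolated by the randomized catheter, an additional atrial lesion outside the four exceptions, and no later recurrence, drug use or re-ablation.

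| Rule | What it tests | Result |
|---|---|---|
| Protocol 6.3.1 and 6.3.2, acute success or failure | Vein isolation with the randomized treatment; modality used for PVI | Success |
| Protocol 7.4, index item | Non-randomized modality used for PVI | Not triggered |
| Protocol 7.4, any-time item | Re-ablation | Not triggered |
| Protocol 3.4.12 and SAP 4.1.12 | Randomized treatment for PVI received as Section 5.2 or 5.3 specifies | Ambiguous: tied to PVI, but cites the section holding the prohibition |
| SAP 16.3 | Four permitted indications | Not counted as a failure |
| Protocol 7.6 item 8 | Other atrial ablation *required* | Unclear: a prohibited lesion was not required |
| SAP 9.3.8 | Extra ablation *received* | Probably excluded; not failed |

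The subject is a success in the primary analysis and in the one analysis that counts extra ablation as failure.

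**2. The plan's own figures.** Inputs from Protocol 9.7 and SAP 11.2: success 0.65 in both arms, margin 0.15, one-sided alpha 0.05, 90% power, 1:1. The Farrington-Manning formula is

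n = [z(0.95)·√V0 + z(0.90)·√V1]² / (pT − pC + 0.15)².

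The restricted null rates are 0.568 and 0.718, so V0 = 0.448; V1 = 2 × 0.65 × 0.35 = 0.455. Then n = (1.645 × 0.669 + 1.282 × 0.675)² / 0.0225 = 171.7, or 172 per arm, as stated. The sample size is not in question.

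**3. Illustrative size.** Rule from SAP 9.1: Beta(0.5, 0.5) priors, margin 0.15, posterior threshold 0.956. I enumerated all binomial outcomes at 225 per arm (N = 450) with control success 0.65, fixed size and no missing data. The null is pT = 0.50.

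If a share f of Pulsed Field subjects, in excess of Thermal, receives prohibited lesions, and a share r of their would-be failures is rescued, the shift at the null is f × r × 0.50. Both f and r are assumptions.

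| Shift in one arm | Example | pT | False non-inferiority |
|---|---|---|---|
| None | equal use and effect | 0.5000 | 0.047 |
| 0.25 point | 2% × 25% × 0.50 | 0.5025 | 0.053 |
| 1 point | 4% × 50% × 0.50 | 0.5100 | 0.073 |
| 2 points | 8% × 50% × 0.50 | 0.5200 | 0.108 |

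For comparison, SAP Table 4 reports 0.0487 for the adaptive design at the same null, so the fixed-size baseline of 0.047 is a fair reference.

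**The case against.** Four points deserve weight.

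- **Another planned analysis exists.** A reader might infer that prohibited ablation carries no consequence and that no planned analysis would reveal it. The documents do not support that. SAP 9.3.8 is not limited to required ablation or to the four indications, and it can remove these subjects and show the resulting difference. This stands. But that analysis is descriptive, excludes rather than fails, and uses a different word from the protocol section it implements.
- **The Per Protocol rule is not silent.** It cites Section 5.2, where the prohibition sits, so one can argue such a subject was not treated as specified. It is equally arguable that the criterion concerns PVI only, and this subject received randomized PVI. The fair description is ambiguous.
- **The prohibition is itself a control.** Deviations must be reported (Protocol 12.13), persistent non-compliance can stop screening at a site (12.12), and endpoint data are fully verified (11.3). Keeping a deviating subject's observed outcome in an as-randomized analysis is also normal. All of this stands and is why the primary definition should not change. None of it supplies the missing sensitivity result.
- **The exceptions imply a failure.** Because 5.2 says the permitted ablations are not failures, a reader might infer that other ablation is one. Section 7.4 governs the endpoint and does not say so.

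**Conclusion.** The point holds as a gap in the supporting analyses, not as an error in the primary test. Protocol 7.4 leaves a prohibited index lesion as a possible Treatment Success, SAP 16.3 checks only the permitted exceptions, and Per Protocol status is unresolved.

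Its size is unknown. Neither the frequency nor the effect of prohibited lesions is given, the rule applies to both arms, and bias arises only if use or effect differs between them. Across the assumed one-arm shifts of 0.25 to 2 points, false non-inferiority runs from 0.053 to 0.108 against 0.047.

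A reader might fix on a single larger figure, such as 0.086 for a 1.4-point shift. That needs, for example, a 5% excess in one arm with 56% of would-be failures rescued (0.05 × 0.56 × 0.50 = 0.014). Nothing in the documents supports either input.

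**What to change.** Leave Protocol 7.4 unchanged and make three wording changes.

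1. **SAP 16.3.** Keep the four listed indications and extend the analysis so that any ablation other than PVI or CTI at the Index / Rescheduled Index Procedure, permitted or not, counts as a failure. Show accessory pathway and AVNRT ablation separately. Do not replace the list with left atrial ablation alone: that would drop permitted right-sided ablation and miss prohibited right atrial lesions beyond the CTI.
2. **Protocol 3.4.12 and SAP 4.1.12.** Add to the Per Protocol exclusions: ablation at the Index / Rescheduled Index Procedure outside the Section 5.2 exceptions.
3. **Protocol 7.6 item 8 and SAP 9.3.8.** Use the same criterion in both: atrial ablation other than PVI or CTI that was *received*.

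**Cost.** Lesion-set data are already collected at the index procedure (Protocol 4.7.2), so no new data are needed. The Per Protocol set may be slightly smaller and the sensitivity result slightly less favourable. As a guide, use a normal approximation at N = 450 with true success 0.65 in both arms. The pass probability is Φ[(pT − pC + 0.15)/SE − 1.706], which is 0.948 with no such subjects. If 5% are recoded as failures, success becomes 0.65 × 0.95 = 0.6175; the pass probability is then 0.942 when this happens in both arms and 0.811 when it happens in the Pulsed Field arm only. The second figure shows the imbalance the analysis is meant to expose.

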### 5.3 Rescheduled Index Procedure

Subjects found during the Index Procedure to have LA thrombus will have their Index Procedure rescheduled to allow treatment of the thrombus, including a minimum of 3 weeks of continuous therapeutic anticoagulation consistent with **Section 5.1**. The Reschedule Index Procedure will follow the requirements of **Section 5.2**.

This rescheduling is permissible and does not create an Acute Procedural Failure. For adjustment of follow-up assessments please see **Section 5.5** below. References to “Index Procedure” in this protocol should be assumed when appropriate to include “Rescheduled Index Procedure” as well if not otherwise specified.

### 5.4 Re-Ablation Procedures

Re-ablation under this protocol requires documentation of Detectable AF, AFL or AT. When performed, re-ablation will be performed utilizing an FDA-approved study ablation catheter (RFA or CBA) at Investigator discretion.

Any re-ablation procedure for AF, AFL or AT any time during study follow-up constitutes a Treatment Failure.

However, CTI ablation or re-ablation for right-sided typical AFL may be performed at any time during study follow-up and does not constitute a Treatment Failure.

Cardiac imaging:

- For anticipated PVI re-ablations occurring Day 1-75, pre-procedural imaging is not required.
- For anticipated PVI re-ablations scheduled for Day 76 or later, ensure the Day 90 cardiac MRI/CT is performed before re-ablation to assess the dimensions of the PVs. The Cardiac CT or MRI scan must be of the same type as the baseline scan obtained prior to the Index / Rescheduled Index Procedure.

TEE within 48 hours of the procedure or ICE during the procedure will be utilized prior to transseptal puncture for exclusion of LA thrombus. If the study reveals atrial thrombus, the investigational procedure will not begin or will be terminated and no ablation will be performed.

Re-ablation does not reset the Blanking Period or otherwise alter the Schedule of Events and Assessments (**Section 4.7**).

Remapping will be performed:

[figure not shown]
- During any re-ablation procedure in which LA access is performed:
  - Sufficient mapping to establish the durability of isolation of each previously treated PV.
- During any re-ablation procedure in a subject who underwent CTI:
  - Sufficient mapping to establish the durability of a previously treated CTI.

## 5.5 Start Date, Blanking Period and Index Procedures

The day of the Index Procedure or Rescheduled Index Procedure is the Start Date (Day 0) for follow-up scheduling. The Blanking Period consists of a subject's Day 0 through and including Day 90. During the Blanking Period, any occurrence of Detectable AF, AFL or AT will be documented; however, occurrences of AF, AFL or AT during this time will not be considered Treatment Failures.

[figure not shown]
For subjects who undergo ablation at the Index Procedure, the follow-up intervals for safety and effectiveness are depicted in **Figure 9** below:

**Figure 9** Index Procedure Blanking and Follow-Up Intervals

For subjects who undergo ablation at a Rescheduled Index Procedure the follow-up intervals for safety and effectiveness are depicted in **Figure 10** below. The follow-up intervals for effectiveness and safety are still based on the day of the ablation procedure (Day 0). Pre-ablation AEs that occur between the Index Procedure and the day before the Rescheduled Index Procedure will not be included in the safety analyses, but will be documented and reported separately, with the day of occurrence being enumerated from the day of the Index Procedure that was deferred.

**Figure 10 Rescheduled Index Procedure Blanking and Follow-Up Intervals**

## 5.6 Roll-In Subjects

Up to 105 subjects – to be treated with the FARAPULSE devices – will be consented and treated in a manner consistent with the Pulsed Field Group but will be analyzed and reported separately from the study population.

At each site, these Roll-In Subjects will be the first 1 to 3 sequentially enrolled but non-randomized subjects at that site. Sites with more than 1 Investigator will utilize available Roll-In Subjects jointly as required.

With Sponsor and Investigator agreement, the Roll-In phase at a site will be terminated at or before 3 Roll-In Subjects have been treated and all subsequent subjects at the site will be randomized as study subjects according to protocol requirements.

Roll-In Subjects will:

- Be consented using a Roll-In-specific ICF.
- Follow the Index Procedures as specified in **Section 5.2**.
- Have all study data gathered as specified in **Section 4.7.2** and **Section 4.7.3**.
- Be followed for 12 months post-ablation, completing Day 7 and Month 3, Month 6 and Month 12 Assessments for clinically-detected arrhythmias and screening for the occurrence of AEs
- Be managed according to Investigator or referring physician discretion.
- Have their required study data recorded on a specific and separate CRF set.
- Be analyzed and reported separately from the ITT Subjects.

Roll-In Subjects will not:

- Undergo Quality of Life assessments
- Undergo NAS assessment
- Undergo protocol-specified EM or Holter monitoring
- Undergo protocol-specified cardiac imaging post-procedure

## 5.7 Blinding

- Investigators: The treating physicians and site-based study personnel are necessarily exposed to a subject's treatment assignment and cannot be blinded. As much as possible, site based study personnel who perform follow-up evaluations will remain blinded to subject treatment assignment.

- Subjects: Study personnel will be trained to avoid disclosing treatment status to study subjects. Study subjects will sign an informed consent that states that they will not be informed of their treatment status until the conclusion of their participation in the study.
- Core Laboratories: The ACL, CICL and Brain Imaging Core Lab (BICL) will remain blinded to treatment assignment throughout the study duration.
- CEC: The CEC will remain blinded as much as possible consistent with accurate adjudication.
- Data and Safety Monitoring Board (DSMB): In general, the DSMB will review unblinded results in order to perform their function of protecting the integrity of the study and the rights, safety and welfare of study subjects.
- Study / CRO staff: Monitoring staff will be unblinded to perform their function. Other Sponsor and CRO staff will be unblinded on a documented need-to-know basis to allow conduct of the study.

## 5.8 Neurologic Assessment Subjects

Neurologic Assessment Subjects (NAS) are a subset of ITT Subjects who will undergo a post-procedural brain MRI following the ablation procedure.

### 5.8.1 NAS Sites

A subset of study sites qualified and willing to perform the standardized brain MRI post-ablation will be established and designated as NAS sites. NAS sites will be selected to generate a minimum of 80 NAS Subjects, balanced approximately equally between RFA and CBA control sites. Total NAS enrollment will be limited to a maximum of 40 subjects in the PFA group and 40 subjects in the Thermal Group (RFA/CBA).

- An approximately equal number of RF-control sites and cryoballoon-control sites will be targeted.
- All ITT Subjects at NAS sites free of contraindications to MRI will be consented for post-procedure MRI until the study enrollment target of evaluable scans is met.
- Roll-In Subjects are excluded from participation in the NAS.

### 5.8.2 Post-Ablation Brain MRI Specifications for NAS Subjects Only

These specification are for the protocol-required brain MRIs of NAS Subjects only.

- Standards and Quality Control: The BICL will establish specific standards for brain MRI performance, train participating sites and interact with sites to ensure that standards and scan quality remain within specification.
- Timing: Post index procedure (between 12 hours to 48 hours post-ablation) brain MRIs will be performed on each NAS subject.
- Parameters: The following scan parameters will be used:
  - 1.5-T scanners
  - 5mm slice thicknesses
  - DWI, FLAIR and ADC assessed for each scan
  - SCE = DWI + and ADC reduced

- SCL = DWI + and ADC reduced and FLAIR +

### **5.8.3 SCE and SCL Analysis**

The frequency and type of SCEs and SCLs will be reported by randomization group, along with potential predictor variables including CHA2DS2-VASC status, duration of PAF, history of stroke/TIA, procedure time, LA dwell time and total ablation time, anticoagulation regimen and ACT levels, occurrence of cardioversion or air introduction, frequency of LA catheter exchanges and maximal sheath size.

### **5.8.4 Follow-Up for Subjects with SCE or SCL Lesions**

- Subjects with a site-confirmed post-procedural SCE or SCL will undergo a pre-discharge neurologic assessment as specified in **Section 4.7.3**.
- Subjects with a site-confirmed or BICL-confirmed post-procedural SCE or SCL will undergo a follow-up brain MRI using the parameters specified in **Section 5.8.2** during the 90 Day Assessment window.

### **5.9 Antiarrhythmic Drugs**

AADs, except for amiodarone, may be utilized during the Blanking Period at the Investigator's discretion.

On Day 60 ± 10 each subject will be contacted by telephone to stop all AADs.

Class I / III AADs (see **Section 6.3.4**) should be stopped at the Day 60 Assessment. However, at the Investigator's discretion, Class I / III AADs may be continued up to Day 90 without creating a Treatment Failure. If AADs are required after Day 90 and Class I / III AADs are prescribed, the Investigator should document the reason for utilizing the medication in the eCRF. Notwithstanding the impact on study outcomes, the use of Class I / III AADs for subject welfare as determined by the Investigator during and after the Blanking Period do not constitute protocol deviations.

The use of amiodarone at any time during the study, except intra-procedurally to control an arrhythmia , or the use of Class I / III AADs after Day 90, constitute a Treatment Failure.

